6.2.10. Study Diary

Distribution of Study Diary

Participants will be provided a study diary at study entry (either electronic or paper).

Participants will be asked to keep a log of symptoms, temperature (if possible), medications they are taking, presence of feverishness, chills, myalgias, headache, sore throat, loss of sense of smell, loss of sense of taste, cough, shortness of breath, and major events such as urgent visit to an emergency room or clinic (including telemedicine) and hospitalization in their study diary. At study entry, study diary information will be recorded prior to study treatment initiation. Starting on Day 2, participants will be asked to complete the diary in the evening.

Review of Study Diary

The study diary will be reviewed by study staff with each participant at the in-person (in-clinic and in-home) visits described in the SOE and the participant's entries will be recorded in the Participant Study Diary eCRF. If feasible, prior to or during the remote study visits, sites will request that the participant send images of each of their study diary entries to be reviewed at the next study contact.

Participants who report worsening illness from any cause during the trial may be referred to their health care provider or closest emergency room. Such instances will be recorded at the time of the notification, and during follow-up to assess study endpoints, (e.g., hospitalization or death).

Review of Treatment Adherence

The treatment adherence diary will be reviewed by study staff with each participant at the inperson (in-clinic and in-home) visits, as described in the SOE. The participant's answers regarding doses taken will be recorded in the Adherence Assessment eCRF. If any doses are missed, the reason for the missed dose will be recorded.

Collection of Study Diary

The study diary will be reviewed per the SOE.

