10.7.3.2. Secondary Outcomes

Safety: Occurrence of Grade 2 or higher AEs and drug related AEs will be evaluated using the same approach as outlined for the primary safety analysis in Section 10.7.3.1. We will describe and estimate all-cause mortality and hospitalization during the 28-day period from and including the day of the first (confirmed) dose of study treatment. The Kaplan-Meier approach described above will be applied to the endpoint of days until first hospitalization or death, and the 28-day risk function will be estimated as described for the primary safety endpoints.

Duration of fever, duration of symptoms, and duration of time to self-reported return to usual health will be summarized with descriptive statistics. Participant-specific durations of fever and symptoms will be compared between study arms using a stratified Wilcoxon rank-sum test. The distribution of days until improvement of all new or worsened COVID-19 symptoms will be compared between study arms using Kaplan-Meier methods with a corresponding exact stratified log-rank test (to account for the "early" versus "late" time from symptom onset randomization strata). New or worsened symptoms of COVID-19 may include feverishness, chills, myalgias, headache, sore throat, loss of sense of smell, loss of sense of taste, cough, and difficulty breathing. Improvement in these symptoms is defined as a decrease in all new or worsened symptoms (i.e., from severe/moderate severity to mild/absent/pre-COVID-19 severity, or a decrease in mild severity to absent). Participants who do not have complete symptom diaries due to hospitalization or death will be ranked in these analyses as having poorer outcomes than participants who survived without hospitalization.

Analyses for the additional objectives will be described in the SAP.

Virologic: The distribution of days until first non-detectable SARS-CoV-2 in NP swabs (i.e., infectious virus measurement) will also be estimated for each randomized arm (drug versus placebo), using Kaplan-Meier methods with a corresponding exact stratified log-rank test (to account for the "early" versus "late" time from symptom onset randomization strata). Participants who prematurely discontinue the study before achieving nondetectable results will have follow-up for efficacy endpoints censored at the date of last measurement. Losses to follow-up will be assumed non-informative.

Protocol EIDD-2801-2003 Ridgeback Biotherapeutics LP

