Time to COVID Symptom Resolution will be derived based on subject overall assessment of COVID symptoms with resolution defined as 3 consecutive assessments in a resolved state. For subjects with mild, no symptoms or no diary data at the baseline, the time to resolution is defined as the first time where subject overall assessment is no symptoms for 3 consecutive assessments . For subjects with moderate or higher severity at the baseline, the time to resolution is defined as the first time where subject overall assessment is mild or no symptoms for 3 consecutive assessments. Subjects who completed study and have reached the resolved state on the last 2 assessments will be considered as resolved on the day prior to the last assessment. Subjects who completed study and have reached the resolved state will be considered as resolved on the last assessment will be considered as resolved on the last assessment will be considered as resolved state on the last assessment will be considered as resolved state on the last assessment will be considered as resolved state on the last assessment will be considered as resolved state on the last assessment will be considered as resolved state on the last assessment will be considered as resolved state on the last assessment will be considered as resolved state on the last assessment will be considered as resolved state on the last assessment will be considered as resolved state on the last assessment will be considered as resolved state on the last assessment will be considered as resolved state on the last assessment will be considered as resolved state on the last assessment will be considered as resolved state on the last assessment will be considered as resolved state on the last assessment will be considered as resolved on the date of the last assessment.

Subjects not achieving symptom resolution and completing the study will be censored at date of last COVID symptom diary. Subjects not achieving the event and dropped out before Day 28 will be censored at Day 28. Subjects who do not achieve the event and do not complete the day 28 diary due to hospitalization will be censored at day 28.

Subject diary data collected within 28 days of first dose will be included in the derivation of the time to COVID symptom resolution endpoint.

Time to resolution (days) = Date of resolution (Censored) – date of first dose+1

• Time to patient reported general physical health of 3 or 4 (Very Good or Excellent)

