5.6. Missing Data and Outliers

For subjects who prematurely discontinue the study, all available data will be included in the analyses. The planned safety and efficacy analyses will be based on the reported data. An investigation will be made concerning the sensitivity of the results if extreme outliers are detected within the data.

Missing data will not be imputed. However, for adverse events with missing onset dates, treatment emergent flags will be assigned based on the imputation below:

Missing Adverse Event (AE) Onset Date

When a missing or partial onset date has been recorded, the following algorithm will be performed, designed to conservatively assign AEs as treatment emergent when the AE end date is not before the date of first dose.

- If the onset date is entirely missing, then the AE will be assigned as treatment emergent.
- If the year of onset only is provided and the year is the same as the year of first dose of any study drug, then this event would be treatment-emergent. If the year of onset only is

provided and the year is not the same as the year of first dose, then the onset date will be imputed as the 1st of January of that year to determine if the event is treatment emergent.

• If the month and year of onset are provided, and the month and year are equal to the month/year of first dose of any study drug, then this event would be treatment-emergent. In all other cases, the 1st day of the provided month/year of onset will imputed for the onset date to determine treatment emergent. Only if the provided month/year of onset is prior to the month/year of first dose would an event **not** be considered treatment-emergent.

AEs with end date prior to the date of first dose will not be considered treatment-emergent.

AEs with missing severity will be excluded from the by severity summaries. TEAEs with missing relationship to study drug will be considered to be probably related to study drug in the summaries.

Missing Data for SARS-COV-2 RNA Undetectable (Negative) Endpoint

Subjects with missing SARS-COV-2 RNA at a visit(s) will be imputed based on the available non missing SAS-COV-2 RNA data described in the table below:

Visit Before	Visit After	Imputation of Undetectable SAS-COV-2 RNA
BLQ/BLD	BLQ or BLD	Negative
>BLQ	BLQ or BLD	Positive
BLQ/BLD or missing	>BLQ	Positive[1]
Missing	BLQ or BLD	Missing
any value	Missing	Missing

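### For the symptom-resolution endpoints, the SAP narrows the protocol's worst-rank rule for diaries left incomplete by hospitalization or death, does not say how a hospital gap affects a run of resolved entries, and does not declare the change

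*SAP*

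**What the plan says.** **Protocol.** Section 10.7.3.2 (Part 1, secondary outcomes) covers the duration of fever and symptoms and the days until all new or worsened symptoms improve. Participants lacking a complete diary because of hospitalization or death "will be ranked in these analyses as having poorer outcomes than participants who survived without hospitalization". Section 6.2.10 makes the diary a daily record: "Starting on Day 2, participants will be asked to complete the diary in the evening".

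**SAP.** Section 5.5.3 builds time to symptom resolution on the participant's overall assessment, with "resolution defined as 3 consecutive assessments in a resolved state". For participants who were moderate or worse at baseline, "the time to resolution is defined as the first time where subject overall assessment is mild or no symptoms for 3 consecutive assessments". Study completers who "reached the resolved state on the last 2 assessments will be considered as resolved on the day prior to the last assessment", and a single resolved final assessment also counts for completers. Hospitalization appears in one sentence: "Subjects who do not achieve the event and do not complete the day 28 diary due to hospitalization will be censored at day 28". Death is not named. The data window is wide: "Subject diary data collected within 28 days of first dose will be included in the derivation". Six further endpoints are derived in the same way: general physical health, return to pre-COVID health, upper respiratory symptoms, the 13-symptom and 12-symptom sets, and cough.

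On gaps, SAP 5.6 says "Missing data will not be imputed". Its tables for filling a missing visit cover viral RNA and infectious virus, not the diary.

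SAP section 1 says that the SAP supersedes the protocol's statistics and that substantial differences will be identified. Section 11 lists two: the unstratified log-rank test and the dropped safety comparisons.

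**The concern.** The protocol's ranking stops a participant who became ill enough for admission, and stopped keeping a diary, from being scored as an ordinary recovery. The SAP sentence protects against this only when two conditions hold together: the participant never meets the event, and the Day 28 diary is missing because of hospitalization. A participant who is admitted, goes home and later records resolved days falls outside it. So does one who recorded three resolved days and was then admitted.

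The missing gap rule adds a second problem. The run is counted in assessments, and nothing says whether a day without an entry is skipped or ends the run. Two programmers could both follow the SAP and date the same participant differently.

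Symptom severity and duration is a secondary objective, and so is the proportion hospitalized. If one arm has more admissions, the SAP rule gives that arm more recoveries than the protocol rule would. If that arm is placebo, a symptom benefit of the drug is understated.

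**Working it through.** The documents give no event count, power figure or hospitalization rate for this endpoint, so there is no planned figure to reproduce. The check applies the rule to invented diaries and then sizes the effect per participant.

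**Step 1. Apply the rule.** All diaries start at moderate, so mild or none counts as resolved. Days in hospital have no entries. *Skip* means that the run is counted over available assessments. *Break* means that it must fall on consecutive calendar days. The event is dated at the first assessment of the run.

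| Diary | Skip | Break | Protocol 10.7.3.2 |
|---|---|---|---|
| A: resolved Day 7; hospital Days 8-15; resolved from Day 16 | Event Day 7 (run 7, 16, 17) | Event Day 16 | Worst rank |
| B: hospital Days 5-12; resolved from Day 13 | Event Day 13 | Event Day 13 | Worst rank |
| C: resolved Days 4-6; hospital Day 7 to Day 28 | Event Day 4 | Event Day 4 | Worst rank |
| D: never resolved; hospital Days 20-28 | Censored Day 28 | Censored Day 28 | Worst rank |
| E: resolved only on Days 7, 16 and 17; hospital Days 8-15 | Event Day 7 | Censored Day 28 | Worst rank |
| F: hospital Days 20-27; first resolved Day 28; completes study | Event Day 28 | Event Day 28 | Worst rank |

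The protocol ranks all six below every participant who survived without hospitalization. Under *skip*, the SAP leaves only D unresolved; under *break*, D and E. Even then they tie with other participants censored at Day 28 instead of ranking below them. B, C and F are events under both readings, so the narrowing does not depend on how gaps are read. A and E show what the gap reading adds: in A the two dates differ by 16 - 7 = 9 days, and in E an event becomes a censoring.

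**Step 2. Effect per participant.** Suppose that there is no censoring before Day 28. Moving *h* participants from an event on Day *t* to no event by Day 28 then lengthens the restricted mean of an arm of *n* by *h* × (28 - *t*)/*n*. Part 1 has about 22 per arm (Protocol 10.5). The event days and the values of *h* are assumptions.

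| SAP event day | h = 1 | h = 2 | h = 3 |
|---|---|---|---|
| 7 | 21/22 = 0.95 days | 1.91 | 2.86 |
| 13 | 15/22 = 0.68 days | 1.36 | 2.05 |
| 16 | 12/22 = 0.55 days | 1.09 | 1.64 |

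**Step 3. How many.** At an assumed 10% with diaries incomplete because of hospitalization, 0.10 × 22 = 2.2 Part 1 placebo participants. One to three participants correspond to 1/22 = 4.5% up to 3/22 = 13.6%.

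**Step 4. Declared or not.** Neither entry in SAP section 11 concerns the symptom endpoints or hospitalization.

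**The case against.** Much of the opposing case stands.

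- **Discharge is not the trigger.** A reader might infer that the SAP counts people as resolved once they leave hospital. It does not. Three resolved assessments are needed, or one or two at the end for completers.
- **Bridging follows from silence.** A reader might take the Day 7 date in diary A as the SAP's definite result. The diary is due daily, so consecutive assessments can mean consecutive scheduled days. The end-of-study rule, which dates a run of two to the day before the last assessment, fits that reading. The ban on imputation does not settle it. Diaries may also be electronic, so a stay need not leave a gap. The documents support only that bridging is not prevented.
- **The protocol rule has limits.** It sits in the Part 1 section, concerns incomplete diaries and not every admission, and was written for improvement of all new or worsened symptoms, not the SAP's overall assessment. Protocol 10.8 has no such ranking for the pooled analyses. Applying it to all 54 planned placebo participants goes beyond the text.
- **No percentage-point effect can be derived.** Assuming 10% hospitalized on placebo and 3% on drug, with everyone improved by Day 28, returns 7 points only because 7 is the difference put in.
- **The stakes are moderate.** SAP 9.3 only summarizes these endpoints by Kaplan-Meier, and the one formal hypothesis test concerns Part 1 viral RNA. Hospitalizations, medical visits and the clinical composite are reported separately.
- **The SAP prevails by design.** This is an undeclared change, not a breach of the hierarchy. The quoted censoring sentence is itself close to the protocol's intent; the difficulty is whom it leaves out.

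What remains is that the rule to be run is weaker than the protocol's safeguard, is open at the gap, and is not listed as a change.

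**Conclusion.** The point holds in a limited form. For Part 1, the SAP replaces a worst rank for diaries left incomplete by hospitalization or death with Day 28 censoring of a subset. It leaves the treatment of hospital gaps undefined and does not declare the change. A hospitalized course can therefore be scored as recovery, and the same rule passes to six further diary endpoints.

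The size cannot be fixed from the documents. For an arm of 22, each affected participant moves the 28-day restricted mean by 0.55 to 0.95 days for assumed event days 16 to 7. One to three participants give 0.55 to 2.86 days. With few admissions the effect is small, and medians may hardly move. A pull toward no difference requires hospitalization to differ between arms in the same direction as symptoms; with equal rates, the main cost is an ambiguous derivation. The documents do not support saying that the comparison is biased by a known amount, or that the SAP instructs programmers to run across a stay.

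**What to change.** 1. In SAP 5.5.3, carry over the protocol rule. A participant whose diary is incomplete because of hospitalization (identified from the Hospitalization CRF, which the SAP already uses for medical visits) or death by Day 28 is treated as not resolved and censored at Day 28. Apply this to all diary-based time-to-resolution endpoints. They will tie with other non-resolvers at Day 28, which is adequate for a 28-day Kaplan-Meier summary.
2. State that a scheduled diary day missing because of hospitalization breaks a run. This settles the dating if any exception to item 1 is kept.
3. In SAP section 11, list every remaining departure from the protocol. This includes any exception for participants who completed three resolved assessments before admission (diary C) and the extension of the rule to the pooled analyses, where the protocol has none.

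If the sponsor prefers the present SAP rule, items 2 and 3 are the minimum.

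The cost is a few sentences and a small programming change, with no new data. Recorded resolution times may lengthen slightly.

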10.3. Objectives and Endpoints

Objectives	Endpoints
Prir	nary
To determine if EIDD-2801 reduces the time to viral RNA negativity. Viral RNA negativity will be determined by RT-PCR of NP swabs.	• Qualitative RT-PCR
To determine the safety and tolerability of EIDD-2801 including 1) any adverse events (AEs) leading to early discontinuation of treatment, 2) study drug-related discontinuation of treatment, 3) new grade 3 or higher AE (not already present at baseline), and 4) study drug-related new grade 3 or higher AE.	 All AEs leading to early discontinuation of treatment Study drug-related discontinuation of treatment New grade 3 or higher AE Study drug-related new grade 3 or higher AE

Secon	ndary
Safety Objective: To compare the incidence of grade 2 or higher AEs and drug-related AEs between treatment arms.	Grade 2 or higher AEsDrug-related AEs
Virologic Objectives:	
• To determine if EIDD-2801 reduces the time (days) to negativity of infectious virus isolation in NP swabs from SARS-CoV-2-infected adults. Infectious virus isolation is determined by isolation in Vero cell line cultures.	 Infectious virus detection in NP swab samples cultured on Vero-cell cultures Infectious virus detection by microfoci assay of NP swab samples cultured on Vero-cell cultures
• To determine if EIDD-2801 reduces the shedding of SARS-CoV-2 RNA in NP swabs compared to placebo as measured by median change in RNA at Treatment Days 3, 5, 7, 14, and 28 as determined by quantitative RT-PCR.	• Quantitative RT-PCR
• To determine if EIDD-2801 increases viral RNA mutation rate. RNA mutation rate is measured by Next Generation sequencing.	• Comparison of spike and RNA dependent RNA polymerase gene sequences using Next Generation sequencing
Clinical Objectives:	Patient reported symptoms
• To determine if EIDD-2801 changes the severity and duration of self-reported symptoms of COVID-19	• Time to improvement of new or worsened symptoms (including feverishness, chills, myalgias, headache, sore throat, loss of sense of smell, loss of sense of taste, cough, and difficulty breathing) as measured by a decrease in all of these symptoms from severe/moderate severity to mild/absent or a decrease in mild severity to absent in symptom diary (Absent or returned to pre- COVID-19 level = 0, Mild =1, Moderate =2, Severe =3).

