Participant Symptom Diary

Symptom diary data will be listed and individual symptom scores will be summarized by treatment and visit. The worst severity at each visit from the individual symptoms will also be summarized by treatment group.

The time to improvement (defined as symptoms becoming 0=absent or 1=mild; if baseline is mild, then improvement is defined as symptoms becoming absent) in all items and by individual item will be summarized using the Kaplan-Meier method and compared between randomization arms using a log-rank test. The median time to improvement and the cumulative probability of improvement over time with 95% confidence intervals will be provided by treatment group. Additional statistical models will be explored to assess the between group difference. Details will be provided in the SAP.

WHO 9-Point Ordinal Scale and COVID-19 Related Medical Visits

Ordinal Scale Clinical Improvement data will be listed and summarized by treatment. If data permit, the time to hospitalization/death will also be derived and summarized using the Kaplan-Meyer method.

The proportion of participants who require additional medical visits (including telemedicine visits and hospitalization) related to COVID-19 will be summarized by treatment group and compared between active drug versus placebo using a risk difference and corresponding 95% CI.

Safety

All safety data will be provided descriptively by dose group and scheduled time of assessment where appropriate. Adverse events will be coded using the Medical Dictionary for Regulatory Activities (MedDRA). An AE is considered treatment-emergent if it begins or worsens in severity after the first dose of randomized study drug. The number and percentage of subjects with treatment-emergent AEs will be tabulated by system organ class (SOC) and preferred term. Additional AE summaries will be provided by severity, drug related AEs, AEs leading to study drug discontinuation, and serious AEs.

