1. INTRODUCTION

This SAP describes the statistical methods to be used during the analysis and reporting for study EIDD-2801-2003.

Study measurements and assessments, planned statistical methods, and derived variables are summarized in this plan. Planned tables, figures, and listings are specified. All decisions regarding final analyses, as defined in this SAP document, have been made prior to locking the database.

This SAP should be read in conjunction with the study protocol and electronic Case Report Form (eCRF). Any further changes to the protocol or eCRF may necessitate updates to the SAP. This SAP supersedes the statistical considerations identified in the protocol; where considerations are substantially different, they will be so identified. If additional analyses are required to supplement the planned analyses described in the SAP, they may be performed and will be identified in the Clinical Study Report (CSR).

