This endpoint will be derived similarly to the time to symptom resolution.

• Time to patient reported returned to the (Pre-COVID) health

This endpoint will be derived similarly to the time to symptom resolution.

• Time to resolution of upper respiratory tract symptoms (based on the worst severity of the 5 symptoms measured: Cough, Shortness of breath, Sore throat, Nasal obstruction and Nasal discharge)

This endpoint will be derived similarly to the time to symptom resolution.

• Time to resolution of common COVID symptoms (based on the worst severity of the 13 symptoms measured: Cough, Shortness of breath, Feeling feverish, Muscle aches, Diarrhea, Vomiting, Nausea, Headache, Sore throat, Nasal obstruction, Nasal discharge, Fatigue and Chills)

This endpoint will be derived similarly to the time to symptom resolution.

• Time to resolution of common COVID symptoms (based on the worst severity of the 12 symptoms measured: Cough, Shortness of breath, Feeling feverish, Muscle aches, Diarrhea, Vomiting, Nausea, Headache, Sore throat, Nasal obstruction, Nasal discharge and Chills)

This endpoint will be derived similarly to the time to symptom resolution.

• Time to resolution of Cough

This endpoint will be derived similarly to the time to symptom resolution.

• COVID related medical visit

A subject is considered to have a COVID related medical visit if the subject meets any of the following:

- 1. Hospitalized based on the Hospitalization CRF or any outpatient medical visit (including telemedicine visits)
- 2. Answered "Yes" to the Diary question 'Sought urgent medical care at an emergency room or clinic'
- 3. Answered "Yes" to the Diary question "Been hospitalized for at least 24 consecutive hours"

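### The protocol's nine-symptom time-to-improvement endpoint and its log-rank comparison are not carried into the SAP, and the SAP does not list this as a change

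*SAP*

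**What the plan says.** Protocol 10.3 lists, under the secondary clinical objectives, "Time to improvement of new or worsened symptoms". The named items are feverishness, chills, myalgias, headache, sore throat, "loss of sense of smell, loss of sense of taste, cough, and difficulty breathing". All of them must improve: severe or moderate to mild or absent, mild to absent.

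For Part 1, Protocol 10.7.3.2 gives the test for this endpoint: "new or worsened COVID-19 symptoms will be compared between study arms using Kaplan-Meier methods with a corresponding exact stratified log-rank test". Participants whose diaries are incomplete through hospitalisation or death "will be ranked in these analyses as having poorer outcomes than participants who survived without hospitalization". The same section compares durations of fever and of symptoms by a stratified Wilcoxon test. For the pooled analysis, Protocol 10.8 says that time to improvement, for all items together and item by item, "will be summarized using the Kaplan-Meier method and compared between randomization arms using a log-rank test".

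SAP 5.5.3 instead defines resolution from the participant's overall assessment of symptoms, held for three consecutive assessments. It then lists six further endpoints to be derived in a similar way: general physical health, return to pre-COVID health, a 5-symptom upper respiratory composite, a composite "based on the worst severity of the 13 symptoms measured", a 12-symptom version of it, and cough. SAP 9.3 says these are summarised by Kaplan-Meier and names no between-group test. Resolution of individual symptoms is optional there.

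SAP section 1 says that the SAP supersedes the protocol's statistical section and that "where considerations are substantially different, they will be so identified". Section 11 lists two changes: an un-stratified log-rank test for time to non-detectable viral RNA, and no statistical comparison of safety endpoints in Part 1.

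**The concern.** Protocol 10.2 says the primary SAP will address the secondary outcome measures. This one has a stated definition and a stated test, and the SAP carries over neither. If the SAP is followed as written, the between-arm comparison of symptom improvement will not be made, and a reader of section 11 would not know that it had been dropped.

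The substitution also changes what counts as recovery. Take a participant whose only remaining symptom is a new, moderate loss of smell. That person has not improved under the protocol, but is resolved on the SAP's 5-, 12- and 13-symptom composites. Section 11 does record the loss of the Part 1 safety comparisons, so its silence on symptoms leaves it unclear whether the missing symptom test was a decision or an oversight.

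**Working it through.** The documents give no sample size, power or effect size for the symptom endpoint, so there is no stated figure to reproduce. The check is a comparison of the texts and a count of items.

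| Feature | Protocol 10.3, 10.7.3.2, 10.8 | SAP 5.5.3, 9.3 |
|---|---|---|
| Basis | Nine named symptoms, all must improve | One overall self-assessment; worst severity over 5, 12 or 13 items |
| Smell and taste | Included | In none of the three lists |
| Restriction | New or worsened symptoms | None stated |
| Duration of improved state | None stated | Three consecutive assessments, with exceptions at the end of follow-up |
| Incomplete diary, hospitalised | Ranked as a poorer outcome | Censored at Day 28 if the event was not reached |
| Incomplete diary, death | Ranked as a poorer outcome | No explicit rule |
| Between-arm test | Exact stratified log-rank (Part 1); log-rank (pooled) | None named |
| Fever and symptom durations | Stratified Wilcoxon (Part 1) | Not mentioned |

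**Overlap of the symptom lists.** I treat shortness of breath as difficulty breathing, muscle aches as myalgias, and feeling feverish as feverishness.

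- 13-symptom composite: 7 of the 9 protocol items (cough, shortness of breath, feverishness, muscle aches, headache, sore throat, chills), plus 6 others (diarrhoea, vomiting, nausea, nasal obstruction, nasal discharge, fatigue). 7 + 6 = 13.
- 12-symptom composite: the same 7, plus 5 (no fatigue). 7 + 5 = 12.
- 5-symptom composite: 3 of the 9 (cough, shortness of breath, sore throat), plus 2 nasal items. 3 + 2 = 5.
- Missing from all three: 9 − 7 = 2, namely smell and taste.

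**Tests and disclosure.** SAP 9.3 names 0 between-group tests for symptom endpoints. Of the 2 changes in section 11, 0 concern symptoms.

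**Hospitalisation and death.** For a participant who never improves, censoring at Day 28 keeps that person in the risk set without an event. In a log-rank test this comes close to the protocol's ranking. The rules part for a participant who met the resolution rule before admission and then has an incomplete diary: an event under the SAP, a poorer outcome under the protocol. They also part for death, unless death is read as dropout, which the SAP does not say.

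**Are smell and taste available?** Protocol 6.2.10 includes both in the diary, and 10.3 gives a 0 to 3 severity scale. The diary form itself is not among the documents.

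**The case against.** The strongest reply is that the change is authorised and the symptom objective survives. Protocol 10.7 and 10.8 say the SAP prevails where the two differ. SAP 2.2.2 keeps patient-reported symptoms as a secondary endpoint. The overall assessment uses similar severity thresholds, and it and the return to pre-COVID health are not tied to a symptom list, so they may reflect smell and taste. SAP 9.3 also summarises individual symptom scores and worst severity by visit. All of this stands, and the SAP cannot be said to have abandoned symptoms. But none of it supplies the protocol's time-to-event endpoint or its comparison, the SAP does not say that the overall assessment covers smell and taste, and a right to prevail does not cancel the undertaking to identify substantial differences.

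A second reply is that the fielded diary may not match the protocol. The SAP's 13 items include six that the protocol's diary list does not name. This is fair, and it limits what can be said about cost. If smell or taste was not graded, however, that is itself a departure to record.

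A reader might infer three stronger points that the documents do not support.

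- *Inflated false-positive risk over seven endpoints.* The SAP plans no tests of them. Cough lies within the 5-item list, which lies within the 12 and then the 13, so they are far from independent. Protocol 10.7.3 openly declares no multiplicity adjustment for Part 1, and 10.8 makes pooled p-values descriptive.
- *A lost lead endpoint.* The protocol does not rank its symptom endpoints either, and gives the nine-item one no lead status.
- *An endpoint that can never be reported.* SAP section 1 allows additional analyses, identified in the study report. The comparison is unplanned, not barred.

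**Conclusion.** The point holds as an undelivered and undisclosed secondary comparison. One protocol-defined endpoint is not derived. Its log-rank test is absent for Part 1 and for the pooled analysis, as is the Part 1 Wilcoxon comparison of durations. The effect on the estimated treatment difference cannot be sized from the documents. The primary virology endpoint is not affected, and in the pooled analysis the lost test would in any case have been descriptive. The matter should be corrected but does not threaten the trial's main conclusion.

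This rests on the symptom equivalences stated above, and on the separate output specifications (SAP 12.1), which are not available, not adding the endpoint or its test.

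**What to change.** 1. Add to SAP 5.5.3 and 9.3 the protocol's time to improvement of all new or worsened symptoms over the nine named items, with a between-arm log-rank test. Make it un-stratified if the strata are dropped, as section 11 already does for viral RNA.
2. State that participants with diaries incomplete through hospitalisation or death are treated as poorer outcomes, as Protocol 10.7.3.2 has it. Without this the restored endpoint is not the protocol's.
3. Keep the SAP's other symptom and health endpoints as supportive.
4. Record in section 11 the new definitions, the three-assessment rule, the Day 28 censoring, and any log-rank or Wilcoxon comparison that stays dropped, with reasons.
5. If the fielded diary did not grade smell and taste, say so in section 11 and derive the endpoint from the remaining protocol items.

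The cost is one more derived variable, from items the protocol says are collected, and a few lines of text. The diary form should be checked before assuming it is that simple. The downside is that smell and taste may recover slowly, so more participants may be censored.
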